1. PROTOCOL SYNOPSIS

Study Title	A phase 2, double-blind, randomized, placebo-controlled study to investigate possible drug-drug interactions between clobazam and cannabidiol (GWP42003-P)
Clinical Study Type	Phase 2
Indication	Epilepsy
Primary Objective	To determine whether GWP42003-P affects the pharmacokinetic (PK) profile of clobazam (CLB) and its primary metabolite N-desmethylclobazam (N-CLB).
Secondary Objective(s)	To assess the safety and tolerability of GWP42003-P in the presence of CLB.
Study Design	
This is a phase 2, double-blind, randomized, placebo-controlled study in 20 patients.
 
Patients will be randomized in a 4:1 ratio to receive 20 mg/kg GWP42003-P or placebo from days 2 to 33.At the end of the treatment period, patients will be given the option of continuing onto an open label extension (OLE) period if the investigator and patient both agree that it is in their best interests. Doses may be adjusted up or down, dependent on investigator opinion, to a maximum of 30 mg/kg/day GWP42003-P. The OLE will last for a maximum of one year or until marketing authorization is granted; whichever is earlier.Patients that do not continue onto the OLE will taper off of GWP42003-P over a 10 day period and will have a telephone follow-up visit four weeks after the end of taper day on Day 71.Day 1 (Visit 2), patients will not be dosed with GWP42003-P/placebo but will continue to take CLB at a stable dose.Day 2 (Visit 2), patients will begin the up-titration with GWP42003-P or placebo to a maintenance dose or an equivalent maintenance dose of 20 mg/kg/day over a period of 10 days (Days 2 to 11).Day 12 (Visit 3), patients will attend the study site to check safety and compliance.After up-titration with GWP42003-P or placebo, the patients will remain on the maintenance dose for 21 days (Days 12 to 32).On Day 34 (Visit 4), patients will be invited to receive GWP42003-P in the OLE period. If the patient enters the OLE period of the study, the patient will continue to take GWP42003-P

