	
as advised by the investigator.
 
• If the patient does not enter the OLE period of the study, the patient will taper off of GWP42003-P by reducing the dose by approximately 10% of the maintenance dose each day until dosing has ceased, with end of taper on Day 43 (Visit 5). 
PK samples will be taken on the day of enrollment (Visit 2, Day 1) and after completing 21 days treatment on GWP42003-P or placebo (Visit 4, Day 33). The PK assessments will therefore capture the following combinations of CLB and GWP42003-P:
 
• First PK Assessment: CLB only.• Second PK Assessment: CLB and GWP42003-P or placebo. 
Each PK assessment should be performed at time points in respect to a morning dose of CLB. The time points are as follows: Pre-dose, 15 min, 30 min, 1h, 1.5h, 2h, 4h, 6h, 12h and 24h. It is expected that the patient will continue to take their CLB as advised by their physician and PK assessments will be scheduled in order to accommodate this dosing schedule. The GWP42003-P/placebo should be taken twice daily immediately following their CLB dose.
 
PK assessments will analyze the amount of CLB, the CLB primary metabolite N-CLB, CBD, CBD major metabolites, Δ^9-tetrahydrocannabinol (THC) and THC major metabolites. Patients will be required to keep a paper diary to note the time and dose of GWP42003-P and CLB administration each morning and evening and to record any adverse events (AEs) that may occur whilst receiving investigational medicinal product (IMP) and any other medications. Patients will also be requested to record the number and type of seizures for each day whilst on the study.

Primary Endpoint	
The primary endpoints of the study are the PK parameters (C_{max}, t_{max}, $AUC_{(0-\infty)}$ $AUC_{(0-t)}$, $t_{1/2}$) of the following analytes:
 
• CLB• N-desmethylclobazam (N-CLB)• CBD• CBD major metabolites
Secondary Endpoint(s)	
To assess the safety and tolerability of GWP42003-P compared with placebo when taken in combination with CLB. Safety and tolerability will be assessed using the following parameters:
 
• AEs• 12-lead Electrocardiogram (ECG)• Clinical laboratory parameters (clinical chemistry, hematology and urinalysis)• Vital signs• Columbia-Suicide Severity Rating Scale (C-SSRS)• Seizure Frequency• Abuse liability

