Patients will be required to keep a paper diary to note the time and dose of IMP and CLB administration each morning and evening and to record any AEs that may occur whilst receiving IMP and any other medications. Patients will also be required to record the number and type of seizures for each day whilst on the study.

A study schema ([Figure 1-1](#)), presented at the end of [Section 1](#), depicts the overall study design. More detailed information on treatment and study procedures are provided in [Section 8](#) and [Section 9](#) respectively.

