8. TREATMENT PROCEDURES

8.1 Investigational Medicinal Product Dosage, Administration and Schedule

The IMP will consist of three types of medication:

- GWP42003-P Oral Solution containing 100 mg/mL CBD.
- Placebo Oral Solution containing excipients.
- Clobazam (patient supplied).

The GWP42003-P/placebo will be presented as an oral solution containing either the active pharmaceutical ingredient and excipients (in the case of GWP42003-P) or only excipients (in the case of placebo). For details regarding GWP42003-P/placebo formulations, see [Section 5](#).

All patients will be weighed during the study visits and the daily volumes of GWP42003-P/placebo solution to be taken during the titration period, and for the remainder of the study, will be calculated and provided to the patient and/or caregiver. Further information on dispensing procedures will be provided in a separate Pharmacy Manual.

Each patient will take their first dose of GWP42003-P/placebo at Visit 2, Day 2 in the clinic. Patients not entering the OLE will take their final maintenance dose of GWP42003-P/placebo at Visit 4 (Day 33) in the clinic. Patients entering the OLE will take their final dose of IMP at Visit 11 (one year after the end of the blinded phase of the study) or sooner (if marketing authorization is granted within one year).

Patients will use their own supply of Clobazam throughout the study. Patients will continue on the dose that they were on at screening for the blinded phase of the study. Clobazam will only be an IMP for the blinded section of the study.

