8.1.1 Dose Administration

GWP42003-P/placebo will be administered orally by the patient or their caregiver twice each day (morning and evening) using the syringe(s) provided.

GWP42003 P/placebo should be taken immediately after the patient's usual CLB administration. The GWP42003-P/placebo should be swallowed, as per the intended commercial therapeutic route, and may be taken with other concomitant medications, as directed by the investigator.

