9.1.10 Pharmacokinetic Analyses

The plasma concentration/time curves of CLB, N-CLB, CBD, CBD major metabolites, THC and THC major metabolites will be assessed at Visit 2 (Day 1 and Day 2) and Visit 4 (Day 33 and Day 34). Patients will be given their daily dose of clobazam at a scheduled time during Visit 2 and Visit 4 and the GWP42003-P/placebo immediately afterwards (Visit 4 only) to facilitate the accurate timing of blood samples required for PK analysis. Blood samples will be taken by either direct venipuncture or an indwelling cannula inserted into a forearm vein at the following times: Pre-dose and, 15 minutes, 30 minutes, 1 hour, 1.5 hours, 2 hours, 4 hours, 6 hours, 12 hours and 24 hours after dosing. The timing of each PK sample will be relative to the morning dose of CLB.

The pre-dose blood sample will be taken within 30 minutes prior to dosing. The allowable window for post-dose blood sample collection is ± 2 minutes up to and including 1 hour post-dose, ± 5 minutes from 1.5 hours up to and including 6 hours post-dose and ± 1 hour at 12 hours and 24 hours post-dose.

In the event of an AE that, in the opinion of the investigator, is related to a concomitant AED, additional blood samples may be collected.

Analysis of all PK samples will be conducted at a central clinical laboratory. Sample volume requirements and processing procedures will be detailed in a separate laboratory manual.

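### AUC(0-∞) is judged against [0.5, 2.0] with clobazam at steady state on both PK days, so it overstates any exposure change; whether an evening dose falls inside the Day 33 window is also unclear

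*Protocol*

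**What the plan says.** **Sampling.** The Synopsis and 9.1.10 time all ten samples, from pre-dose to 24 h, from one clobazam dose: "Each PK assessment should be performed at time points in respect to a morning dose of CLB". The 12 h and 24 h samples have a window of ±1 h. Patients keep their own clobazam regimen, and "PK assessments will be scheduled in order to accommodate this dosing schedule".

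**Steady state.** Criterion 6.1.6 requires stable antiepileptic drugs, including clobazam, for four weeks before screening and through the blinded phase. Section 3.1 of Amendment 1 says clobazam needs up to 14 days to reach steady state, and lengthens maintenance to 21 days for that reason.

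**Calculation and decision.** Section 13.6.3 (Version 1) gives AUC(0-∞) as AUC(0-t) plus C_last/λz. λz comes from log-linear fits after the maximum to the last three, four, five or more quantifiable points, keeping the fit with the largest adjusted R². The Version 2 Synopsis judges Cmax, AUC(0-t) and AUC(0-∞) of clobazam and N-CLB by a 90% CI against [0.5, 2.0]. Section 4.1.1 makes t1/2 and AUC(0-∞) primary for clobazam, N-CLB, CBD and the CBD metabolites.

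**Dosing on Day 33.** The Synopsis has patients on "20 mg/kg GWP42003-P or placebo from days 2 to 33", and 8.1.1 has it taken "twice each day (morning and evening) using the syringe(s) provided". But 9.2.1.4.1 has patients hand back all supply at the Day 33 visit, 9.1.14 lists the next dispensing on Day 34, and 8.1 places the last maintenance dose of "GWP42003-P/placebo at Visit 4 (Day 33) in the clinic".

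**Clobazam frequency.** Eligibility caps the daily dose at 20 mg and does not restrict frequency. Section 9.1.10 reads as once daily ("Patients will be given their daily dose of clobazam at a scheduled time during Visit 2 and Visit 4"). The Synopsis ("The GWP42003-P/placebo should be taken twice daily immediately following their CLB dose") and the diary instruction in 4.1 ("note the time and dose of IMP and CLB administration each morning and evening") allow for an evening dose.

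**The concern.** After a single dose, AUC to infinity measures exposure. At steady state, the AUC over one dosing interval does. Adding C_last/λz to a full interval counts drug left over from earlier doses, and that amount depends on clearance, the quantity an interaction would change. The Day 33 to Day 1 ratio then no longer estimates the exposure ratio, and the [0.5, 2.0] boundary acts as a tighter one on AUC(0-∞) than on AUC(0-t). The same data could pass on one AUC and fail on the other.

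The second issue is separate. The fit always includes the last three quantifiable points, normally 6, 12 and 24 h. Any dose of the same drug taken between the first and last of these puts two dosing cycles into one slope.

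**Working it through.** The protocol gives no power or precision figure for this point, so there is nothing to reproduce. The formulas are those of 13.6.3 at the protocol's ten sampling times. One compartment, the half-lives and ka are assumptions. The top half-life of 67 h is 14 days divided by five half-lives (336/5).

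**1. AUC(0-∞) at steady state, clobazam once daily.** With interval τ = 24 h and elimination rate k:

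- AUC over one interval = dose/CL (bioavailable dose).
- C_last/k ≈ (dose/CL) × g(k), where g(k) = [ka/(ka − k)] / (e^(kτ) − 1).
- So AUC(0-∞) = (dose/CL) × [1 + g(k)].

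If clearance falls by a factor R with volume fixed, k becomes k/R, and the AUC(0-∞) ratio is R × [1 + g(k/R)] / [1 + g(k)]. With R = 1.5 and ka = 1.5/h:

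| Half-life (h) | 1 + g(k) | 1 + g(k/1.5) | AUC(0-∞) ratio | AUC(0-t) ratio (simulated) |
|---|---|---|---|---|
| 18 | 1.675 | 2.194 | 1.96 | 1.494 |
| 36 | 2.725 | 3.796 | 2.09 | 1.499 |
| 67 | 4.573 | 6.581 | 2.16 | 1.500 |

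Running the fit and the linear trapezoid on noise-free profiles gives the same AUC(0-∞) ratios. As half-life grows against the interval, g(k) tends to 1/(kτ) and the ratio tends to R² (1.5² = 2.25).

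- **Where it crosses 2.0.** AUC(0-∞) reads 2.0 at a true ratio of 1.52, 1.47 and 1.44 for half-lives of 18, 36 and 67 h.
- **Room for the CI.** At a reading of 1.96 the upper 90% limit may exceed the estimate by only 2.0/1.96 = 1.02 before the criterion fails.
- **Direction.** Once daily, a true ratio of 0.67 reads 0.47 to 0.54, and a true 2.5 reads 4.85 to 5.80. The movement is away from 1. In simulation with no interaction and 5% error per concentration, the mean log ratio stayed within ±0.02 of zero.

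**2. What twice-daily clobazam would add.** With the evening dose just after the 12 h sample, a true 1.5 reads 2.17, 2.20 and 2.22. The addition is 2.17 − 1.96 = 0.21 at 18 h and 2.22 − 2.16 = 0.06 at 67 h. AUC(0-t) reads 1.55, 1.53 and 1.51, and AUC(0-12) reads 1.499 to 1.500.

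**3. Terminal fit across a second dose.** Twice daily at steady state, with the second dose just after the 12 h sample, the 24 h level equals the 12 h level. Relative to the extrapolated start, ln C has fallen by 4k, 6k, 12k and 12k at 4, 6, 12 and 24 h. The mean time is 11.5 h, Sxx = 56.25 + 30.25 + 0.25 + 156.25 = 243, and Sxy = −(33.75 + 13.75 + 1.75 + 43.75)k = −93k. The slope is −(93/243)k, so half-life is overstated by 243/93 = 2.61.

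The full rule for CBD (half-life 6 to 60 h) gives:

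| ka (/h) | t1/2 factor, evening dose after the 12 h sample | t1/2 factor, evening dose held past 24 h |
|---|---|---|
| 0.5 | 3.87 to 3.90 | 1.03 |
| 1.0 | 2.66 | 1.00 |
| 1.5 | 2.27 to 2.62 | 1.00 |

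In the first case CBD AUC(0-∞) is 1.24 to 3.23 times what the true slope would give.

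**The case against.** **CBD on Day 33.** A reader might infer that CBD half-life is wrong in every GWP42003-P patient. The documents do not support that. Supply is handed back on Day 33 and next dispensed on Day 34, the Synopsis counts maintenance as Days 12 to 32, and 8.1 puts the last maintenance dose in the clinic on Day 33. Together these allow a morning-only reading, under which the fit is within about 3% of the true half-life. Twice-daily dosing and treatment to Day 33 point the other way. What stands is a conflict in the text.

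**Twice-daily clobazam.** It is permitted, not prescribed, and the number of users could be zero. The main result does not need it.

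**Direction.** A reader might infer that an interaction could be hidden. It could not by this route: the error pushes AUC(0-∞) away from 1, and Cmax and AUC(0-t) are little affected. The CBD parameters enter no decision rule.

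**Source.** The calculation rule is read from Version 1. Version 2's own 13.6.3 is not in the text available. The Amendment 1 entry for that section is an extract that shows changes to the analyte list and the treatment label only, so continuity is inferred. Which samples may enter λz is often left to an SAP. The AUC(0-∞) formula and its use against [0.5, 2.0], however, are fixed in the protocol.

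**Assumptions.** The sizes depend on an assumed model, and no N-CLB figure was computed. The steady-state argument carries over to N-CLB, but its size does not.

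**Conclusion.** The main point holds. As written, AUC(0-∞) is the wrong exposure measure for two PK days at steady state. Over the assumed half-lives of 18 to 67 h, a true clobazam ratio of 1.5 reads 1.96 to 2.16 with once-daily dosing, and the upper boundary is reached at a true ratio of 1.44 to 1.52. The consequence is a possible failure on AUC(0-∞) alone for a moderate interaction inside the boundary, not a missed interaction.

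The secondary point holds as an ambiguity. If a second dose is taken inside the 24 h window, half-life for that drug comes out about 2.3 to 3.9 times too long (ka 0.5 to 1.5/h). How many patients this touches, for CBD or clobazam, cannot be told from the documents.

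**What to change.** **13.6.3 and the Synopsis.** Judge the clobazam and N-CLB exposure ratio on AUC over one clobazam dosing interval (0 to 24 h once daily, 0 to 12 h twice daily) in place of AUC(0-∞). Exclude from λz any sample taken after a second dose of the parent drug.

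**9.1.10.** State whether the Day 33 evening GWP42003-P/placebo dose is taken. Either hold it until after the 24 h sample, which keeps CBD half-life estimable, or give it after the 12 h sample. In all cases draw the 12 h sample before any evening clobazam or IMP dose.

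**Cost.** A few sentences, with no added samples or visits. Holding the evening dose means one delayed or omitted IMP dose. Where a second dose is taken, t1/2 and AUC(0-∞) may not be reportable: with the maximum at 4 h, only the 6 and 12 h samples remain, too few for a three-point fit. The exposure interval would differ between once- and twice-daily clobazam users, but not within a patient's own ratio.

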13.6.3 Pharmacokinetics

Calculation of PK parameters will be based on actual blood sampling times [h] (relative to the corresponding administration time) rounded to two decimal digits with negative pre-dose times set to zero. Plasma concentrations of CLB, N-CLB, CBD and

the major metabolites will be displayed graphically, summarized and listed. For descriptive statistics, values below the lower limit of quantification of the assay (LLOQ) will be excluded from any calculations. Descriptive statistics of concentrations will be calculated if at least half of the individual data points that have been measured are equal to or above the LLOQ.

For calculation of the PK parameters, the following rules will be applied:

At time zero and at time points in the lag-time between time zero and the first quantifiable concentration, concentrations below the LLOQ will be set to zero. All other concentrations below the LLOQ will not be used in calculations.

Variables derived from plasma concentrations:

- Concentration maximum (C_{\max}): Highest observed plasma concentration of the measured concentration-time profile. Dimension: [amount / volume].
- Terminal half-life $t_{1/2} = \ln(2)/\lambda_z$.
- The rate constant of the terminal phase λ_z will be determined by linear regression of log-transformed concentration data after the time of maximum concentration. A sequence of terminal elimination rate constants will be created by linear regression. Linear regressions are repeated using the last three points with a quantifiable concentration, the last four points, the last five points etc. For each regression, an adjusted R^2 is computed. The regression with the largest adjusted R^2 is selected to estimate the terminal half-life. Dimension: [time].
- Area under the concentration-time curve from administration until the last sampling point (t) equal or above the LLOQ $AUC_{(0-t)}$ will be calculated by the linear trapezoidal formula. Dimension: [time • amount / volume].
- Area under the concentration-time curve extrapolated to infinity: $AUC_{(0-\infty)} = AUC_{(0-t)} + C_{\text{last}}/\lambda_z$ and C_{last} is the concentration observed at the last time point with a quantifiable concentration, λ_z refers to the terminal elimination rate constant. Dimension: [time • amount / volume].
- Time of maximum concentrations: T_{\max} will be taken as the time after administration at which C_{\max} occurs. Dimension: [time].

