Table of Appendices

APPENDIX 1.	Schedule of Assessments	87
APPENDIX 2.	Study Personnel	90
Appendix 3.1	Investigator Details	90
Appendix 3.2	Sponsor Contact Details	90

List of In-text Tables

Table 3.3.1-1	Epidiolex Adverse Events.....	32
Table 5.1-1	Formulation of GWP42003-P Oral Solution	35
Table 5.2-1	Formulation of Placebo Oral Solution	35
Table 8.1.2-1	Dose Up-Titration Regimen*	42
Table 9.1.9-1	Hematology, Biochemistry, Urinalysis and THC Screen	47

List of In-text Figures

Figure 1-1	Study Design and Treatment Schema	16
Figure 1-2	Study Design and Treatment Schema	17
Figure 9-1	Flow Diagram for Identifying and Evaluating Clinical Trial Adverse Event Data Through Systematic Categorization Tabulation and Analysis which can Illuminate an Abuse Potential Signal.....	55

List of Abbreviations

AE	Adverse Event
AEDs	Antiepileptic Drugs
ALT	Alanine aminotransferase
AST	Aspartate aminotransferase
AUC _(0-∞)	Area under the concentration time curve from zero to infinity with extrapolation of the terminal phase
AUC _(0-t)	The area under the plasma concentration versus time curve, from time zero to 't' (where t = the final time of positive detection) as calculated by the linear trapezoidal method
BP	Blood Pressure
CLB	Clobazam
CBD	Cannabidiol
CI	Confidence Interval
CIOMS	Council for International Organizations of Medical Sciences
CLB	Clobazam
C _{max}	Maximum measured plasma concentration
CRF	Case Report Form
CRO	Contract Research Organization
C-SSRS	Columbia-Suicide Severity Rating Scale
EC	Ethics Committee
ECG	12-lead Electrocardiogram
EU	European Union
GCP	Good Clinical Practice
GW	GW Research Ltd
GWP	GW Pharma Ltd
IB	Investigator Brochure
ICH GCP	International Conference on Harmonization Tripartite Guideline for Good Clinical Practice
IMP	Investigational Medicinal Product
IND	Investigational New Drug
INR	International Normalized Ratio
IRB	Institutional Review Board
ITT	Intention to Treat

IVRS	Interactive Voice Response System
LOCF	Last Observation Carried Forward
MMRM	Mixed-effects Model Repeated Measures
N-CLB	N-desmethylclobazam
OLE	Open label extension
PBPK	Physiologically-based pharmacokinetic interactions
PI	Principal Investigator
PP	Per Protocol
PVD	Pharmacovigilance Department
SAE	Serious Adverse Event
SAP	Statistical Analysis Plan
SUSAR	Suspected Unexpected Serious Adverse Reaction
$t_{1/2}$	Terminal half-life
TBL	Total bilirubin
THC	Δ^9 -tetrahydrocannabinol
t_{max}	Time to the maximum measured plasma concentration
ULN	Upper Limit of Normal

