4.1.1 Primary Endpoint

The primary endpoints of the study are the PK parameters (C_{max} , t_{max} , $AUC_{(0-\infty)}$, $AUC_{(0-t)}$, $t_{1/2}$) of the following analytes:

- CLB
- N-CLB
- CBD
- CBD major metabolites

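### AUC(0-t) for CBD, THC and their metabolites runs across an unsampled second dosing interval, so it measures neither one interval nor a day's exposure

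*Protocol*

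**What the plan says.** The synopsis, section 4.1 and section 9.1.10 of Protocol Version 2 give the same ten sampling times, counted from the morning clobazam (CLB) dose: "The time points are as follows: Pre-dose, 15 min, 30 min, 1h, 1.5h, 2h, 4h, 6h, 12h and 24h". Section 9.1.10 allows a window of plus or minus one "hour at 12 hours and 24 hours".

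On dosing, the synopsis states: "The GWP42003-P/placebo should be taken twice daily immediately following their CLB dose". Section 8.1.1 confirms morning and evening administration.

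The List of Abbreviations defines AUC(0-t) as the area "from time zero to 't' (where t = the final time of positive detection) as calculated by the linear trapezoidal method". The available Version 2 text stops before section 13.6.3. Version 1 of that section has the same rule: "Area under the concentration-time curve from administration until the last sampling point (t) equal or above the LLOQ". The amendment's entry for 13.6.3 changes only the analyte list and the treatment term.

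Section 4.1.1 says "The primary endpoints of the study are the PK parameters" and lists Cmax, tmax, AUC(0-∞), AUC(0-t) and half-life for CLB, N-CLB, CBD and CBD major metabolites. Section 4.1.2 makes the same parameters secondary for THC and its major metabolites.

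The frequency of CLB is not fixed. The diary is to record CLB each morning and evening, but section 9.1.10 says "Patients will be given their daily dose of clobazam at a scheduled time".

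**The concern.** Because t is the last detectable time, AUC(0-t) runs to 24 h whenever the 24 h sample is quantifiable. For a drug taken every 12 hours that period holds two dosing intervals. The first is profiled by nine samples from pre-dose to 12 h. The second is represented by one straight line from the 12 h value to the 24 h value. Whatever the evening dose does between those points goes unseen.

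The result is a named primary parameter that is neither the exposure of one dosing interval nor that of a day. Its error also depends on how each site times the evening dose. Seven centers are expected, so patients handled differently would give AUCs that are not comparable.

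**Working it through.** The protocol states no AUC, half-life or bias figure, so there is none to reproduce. It supplies the sampling times, the twice-daily dosing and the trapezoid rule. All kinetic values below are assumptions.

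**Step 1: algebra when both late samples are troughs.** Assume steady state, 12-hourly equal doses, and 12 h and 24 h samples each drawn just before a dose. The true 24 h area is 2 × 12 × Cavg. The computed area is 12 × Cavg + 12 × Ctrough, if 0-12 h is captured well. Then

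relative bias = (12·Cavg + 12·Ctrough) / (24·Cavg) − 1 = −0.5 × (1 − Ctrough/Cavg).

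| Ctrough/Cavg | Bias |
|---|---|
| 0.9 | −5% |
| 0.7 | −15% |
| 0.5 | −25% |
| 0.3 | −35% |
| 0.1 | −45% |

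**Step 2: where the evening dose falls.** One-compartment oral profiles were built by adding past doses. Each contributes ka/(ka − k) × [exp(−k·s) − exp(−ka·s)] at time s after the dose, with k = ln 2 / half-life. The linear trapezoid on the protocol's ten times was compared with the exact AUC(0-24). Results for ka = 1 per hour:

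| Half-life | Dose just after 12 h sample | Dose at 11 h, sample at 12 h | Evening dose withheld |
|---|---|---|---|
| 3 h | −36% | +19% | +7% |
| 6 h | −23% | +5% | +4% |
| 12 h | −13% | +1% | +2% |
| 24 h | −7% | 0% | 0% |
| 36 h | −5% | 0% | 0% |

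Over ka 0.3-2 per hour and half-life 3-36 h, the ranges are −38% to −3%, about −7% to +38%, and 0 to +7%.

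**Step 3: which case applies.** The text does not settle it. No available passage puts the 12 h sample before the evening dose. Whether a Day 33 evening dose is taken is also unclear:
- The synopsis gives treatment as Days 2 to 33 but maintenance as Days 12 to 32.
- Section 8.1 says "Patients not entering the OLE will take their final maintenance dose of" GWP42003-P/placebo at Visit 4 (Day 33) in the clinic, without saying morning or evening.
- Section 9.2.1.4.1 has all GWP42003-P/placebo returned on Day 33.
- Section 9.1.14 has it dispensed again on Day 34.

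**Step 4: CLB ratio, if CLB is twice daily.** The calculation was repeated for both PK days, with clearance halved on the second (true ratio 2.0), ka 1-2 per hour, and the evening dose after the 12 h sample. The computed 24 h ratio is about 2.14-2.16 at a 12 h half-life, 2.05 at 36 h and 2.03 at 70 h, an error of about 1-8%. At a true ratio of 1.0 the error cancels. AUC(0-12) ratios are right to within 0.3%.

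**Step 5: the replacement.** With the 12 h sample before the evening dose, the computed AUC(0-12) is within about −1% to +4% of the true interval AUC on the Step 2 grid. If the sample instead follows a dose at 11 h, AUC(0-12) can be about 54% too high (ka 2 per hour, half-life 3 h). The replacement therefore needs the sample-before-dose rule.

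**The case against.** The strongest reply is that nothing is decided on the affected quantities. The primary objective concerns CLB and N-CLB, and the 90% CI no-effect rule covers only those two. Day 1 has no GWP42003-P dosing, so the CBD AUC has no comparator and is only summarised; its primary status is a label. This stands, and it limits the severity.

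A reader might infer that the CBD AUC is systematically understated, by something like 5-35%. The documents do not support that. They give no half-life, absorption rate or trough-to-average ratio for CBD, THC or their metabolites, so any percentage is assumed. The sign is open too, because it turns on an evening dose that the text does not place.

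A reader might also infer that the clobazam conclusion is compromised. That needs twice-daily clobazam, which the diary wording suggests and section 9.1.10 leaves in doubt. Even then the error is small. The amendment rationale says clobazam takes up to 14 days to reach steady state. At four to five half-lives that allows 336/5 = 67 h to 336/4 = 84 h, where a true ratio of 2.0 computes as 2.02-2.03. At a true ratio of 1.5 the computed value is 1.52-1.58 for half-lives of 12-36 h, well inside the limits of 0.5 and 2.0. For true ratios above 1 the bias is upward, away from a false claim of no effect.

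**Conclusion.** The point holds in a limited form. The protocol itself fixes a sampling schedule, a dosing frequency and an AUC rule that do not fit together for CBD, THC and their metabolites. Where t reaches 24 h, AUC(0-t) is not an interpretable exposure measure.

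Under the assumed kinetics it may be about 3-38% too low, about 7% too low to 38% too high, or 0-7% too high, according to whether the evening dose follows the 12 h sample, precedes it by an hour, or is withheld. What the text supports is an undefined error, not a known understatement.

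The consequence falls mainly on descriptive CBD and THC exposure. The CLB/N-CLB ratio is affected only if clobazam is taken twice daily, and then by about 1-8% at a true ratio of 2.0 (assumed half-life 12-70 h). The point is minor to moderate: worth correcting because the parameter is named as primary and the repair is cheap, but no threat to the main conclusion.

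**What to change.** - For CBD, THC and their metabolites, define the AUC as the dosing-interval AUC(0-12) from the existing pre-dose to 12 h samples, in the synopsis and sections 4.1.1, 4.1.2 and 13.6.3.
- State that the 12 h PK sample is drawn before any evening dose, and that actual dose and sample times are recorded.
- For CLB and N-CLB, use the dosing interval that matches the patient's regimen: 12 h if twice daily, 24 h if once daily. Use the same interval on Day 1 and Day 33.
- Reconcile the passages on whether GWP42003-P/placebo is taken on the evening of Day 33 (synopsis and sections 8.1, 9.1.14 and 9.2.1.4.1).
- Say how AUC(0-∞) is handled. Version 1 builds it on AUC(0-t), so it carries the same error and AUC(0-12) alone does not repair it.

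No new samples or assays are needed; the cost is wording and one sampling instruction to sites. The drawback is that clobazam AUC may be reported over two interval lengths. That cancels in the within-patient ratio, but the absolute values would need to be shown by regimen.
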